3.1.3. Study Endpoints

The endpoints for this study include the following:

- Safety parameters:

Serious adverse events, TEAEs, physical examination findings, vital sign measurements, standard clinical laboratory parameters (including serum chemistry, hematology, urinalysis, and coagulation parameters), and electrocardiogram (ECG) parameters.

Other safety parameters will include bleeding events and neurologic function. Bleeding events will be assessed and categorized as sICH, any intracranial hemorrhage (ICH), or non-ICH major bleeding. Neurologic function will be measured using the NIHSS.

- Pharmacokinetic parameters:

Standard noncompartmental PK parameters will be assessed. Plasma samples for PK assessments will be taken at multiple timepoints in the study. Additionally, a PK sample may also be obtained outside of the specified timepoints during the study if deemed clinically necessary. Urine PK samples will also be collected and evaluated in the study.

- Pharmacodynamic parameters:

Pharmacodynamic analysis for TAFIa antigen and clot lysis along with D-dimer and total TAFIa activity will be performed. Remaining blood samples will be used for post-hoc TAFIa inhibition-related coagulation biomarker assessments.

Recanalization will be assessed during the study.

- Other parameters:

An assessment of functional outcome using the mRS will be performed during the study.

3.1.4. Duration of the Study

The study duration is expected to be approximately 15 months.

3.1.5. Duration of Subject Participation

Each randomized subject will receive a single, IV infusion (administered over 6 hours) of DS-1040b or placebo on Day 1. Subjects will remain hospitalized for at least 24 hours after the start of infusion. After 24 hours, the Principal Investigator may discharge the subject at his/her discretion after completing early discharge procedures (Section 6.5). Subjects will return to the clinic on Day 30 \pm 7 days for follow-up assessments. A follow-up assessment on Day 90 \pm 7 days will be conducted by phone.

3.1.6. Stopping Rules

The following criteria will be used to stop dose escalation during the study:

Symptomatic intracranial hemorrhage within 36 hours following the start of infusion:

- 2 cases of sICH in active-treated subjects per dose level
- 4 cases of sICH in active-treated subjects cumulatively across dose levels

Other major bleeding (non-ICH) during hospitalization and up to 5 days following the start of infusion:

- 2 cases of major bleeding defined as Thrombolysis in Myocardial Infarction (TIMI) in active-treated subjects per dose level

Other:

- In addition, DSPD, the PAREXEL Medical Monitor, and the Investigator may decide to halt dose escalation under other circumstances, such as data indicating organ toxicity, even if it is not covered by any of the prespecified stopping rules.

If any of the above criteria are met within a dose group (or across dose groups for sICH), escalation to a higher dose level will not proceed. Following an in depth review of all safety data available across the study, one of the following recommendations will be made:

- Terminate the study.
- Continue with the study but at a modified dose (eg, a dose between the current dose and the previous lower dose).
- Continue with the study but expand either the current or next cohort by an appropriate number (8 to 16) of subjects for more detailed safety evaluation.

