3.1.2. Treatment Groups

This study will consist of 5, sequential, ascending-dose cohorts. A total of 64 to 80 subjects with AIS will be enrolled: 8 to 16 subjects each in Cohorts 1 and 2, and 16 subjects each in Cohorts 3, 4, and 5. In each dose cohort, subjects will be randomized to DS-1040b or placebo in a 3:1 ratio. The Principal Investigator and the subject will be blinded to the subject's assignment to either DS-1040b or placebo. Each subject will receive a single, IV infusion of DS-1040b or placebo. The single, IV infusion will consist of an initial loading dose (25% of the total dose) administered as a 0.5-hour infusion, followed by a maintenance dose (75% of the total dose) administered as a 5.5-hour continuous infusion. The planned dose level for each cohort is listed below in Table 3.1.

Table 3.1: Treatment Groups

Cohort	Number of Subjects	DS-1040b Treatment per Subject
1	6 (or 12) ^a	0.6 mg: loading dose of 0.15 mg IV infusion over 0.5 hour, followed by a maintenance dose of 0.45 mg IV infusion over 5.5 hours
	2 (or 4) ^a	Placebo
2	6 (or 12) ^a	1.2 mg: loading dose of 0.3 mg IV infusion over 0.5 hour, followed by a maintenance dose of 0.9 mg IV infusion over 5.5 hours
	2 (or 4) ^a	Placebo
3	12	2.4 mg: loading dose of 0.6 mg IV infusion over 0.5 hour, followed by a maintenance dose of 1.8 mg IV infusion over 5.5 hours
	4	Placebo
4	12	4.8 mg: loading dose of 1.2 mg IV infusion over 0.5 hour, followed by a maintenance dose of 3.6 mg IV infusion over 5.5 hours
	4	Placebo
5	12	9.6 mg: loading dose of 2.4 mg IV infusion over 0.5 hour, followed by a maintenance dose of 7.2 mg IV infusion over 5.5 hours
	4	Placebo

IV = intravenous.

a: Cohort 1 and 2 will start with an initial cohort of 8 subjects (6 active and 2 placebo). An expansion cohort of another 8 subjects (6 active and 2 placebo) may be added during the study.

Dosing in the successive cohort will occur only after completion of the blinded safety data review (up to discharge) from the previous dose cohort. Upon completion of this

blinded safety data review, a dose escalation decision will be made and the dose of the next cohort may be modified (reduced or repeated). Unblinded data will also be used by the Sponsor to perform PK and PD data analysis during the study.

Dose escalation based on symptomatic intracranial hemorrhage (sICH) criteria will be conducted in the following manner:

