Cohort 1 will start with 8 subjects (6 active and 2 placebo; Cohort 1a). If no sICH is observed in the 6 active-treated subjects, Cohort 2 will start after the dose escalation safety data review. If 1 instance of sICH is observed in 1 of the 6 active-treated subjects of Cohort 1a, an expansion cohort (Cohort 1b) of 8 subjects (6 active and 2 placebo) will be enrolled and treated at the same dose level as Cohort 1a. If no sICH is observed in Cohort 1b, Cohort 2 will start after the dose escalation data review. If 1 sICH is observed in Cohort 1b, the predefined stopping criteria of sICH (2 out of 12 active-treated subjects) will be considered met and no further dose escalation will occur (refer to Section 3.1.6).

Cohort 2 will be conducted in the same manner as Cohort 1.

In Cohorts 3, 4, and 5, 16 subjects will be enrolled in each cohort. Within each cohort, if sICH is observed in 2 out of 12 active-treated subjects, sICH stopping criteria will be considered met and no further dose escalation will occur. Following an in-depth safety data review, the study may be terminated or continued with a modified (lower) dose.

Additionally, if 4 or more cases of sICH in the active-treated subjects are observed across all completed cohorts at any time during the study, the stopping criteria for sICH will be considered met and no further dose escalation will occur; however, the study may proceed at a lower dose.

Each randomized subject will receive a single, IV infusion (administered over 6 hours) of DS-1040b or placebo on Day 1. Subjects will remain hospitalized for at least 24 hours after the start of the infusion. After 24 hours, the Principal Investigator may discharge the subject at his/her discretion after completing early discharge procedures (Section 6.5). Subjects will return to the clinic on Day 30 ± 7 days for follow-up assessments. A follow-up assessment on Day 90 ± 7 days will be conducted by phone.

For additional details of the study procedures and the Schedule of Events see Section 6 and Section 17.5, respectively.

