11.10. Sample Size Determination

The sample size for this study is not based on statistical power calculations. The number of subjects at each dose level is considered sufficient to achieve the primary objective of this study.

At least 8 subjects each will be enrolled in the first 2 cohorts. An additional expansion cohort of 8 subjects may be added during the first 2 cohorts if additional information is needed in order to move forward with the last 3 cohorts. At least 16 subjects each will be enrolled in the last 3 cohorts: 12 of which will be randomized to active treatment, and 4 to placebo treatment. A stopping rule of sICH is predefined: 2 cases of sICH in 12 active-treated subjects per dose level, or 4 cases of sICH in active-treated subjects cumulatively across dose levels. This sample size and stopping rule are determined in consideration of sICH observation and dose escalation criteria in small dose cohort safety studies conducted with tissue plasminogen activator.^{3,4} The incidence of sICH observed is about 16% per dose level in these studies. The sample size and stopping rule of sICH in current study are designed to prevent a greater incidence of sICH than observed with tissue plasminogen activator in small dose cohort safety studies.

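### After an sICH stop in Cohorts 3 to 5, Section 3.1.2 names only termination or a lower dose, while Section 3.1.6 also permits expansion at the same dose

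*Combined protocol and SAP*

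**What the plan says.** Section 3.1.2 (Treatment Groups) treats 2 sICH among the 12 active subjects of Cohort 3, 4 or 5 as meeting the stopping criterion. Escalation ends and, after a safety review, "the study may be terminated or continued with a modified (lower) dose". For the cumulative criterion of 4 or more cases, "no further dose escalation will occur; however, the study may proceed at a lower dose". Neither sentence mentions expansion, and neither refers to Section 3.1.6. The text for Cohort 1 does refer to it, and Cohort 2 is run in the same way as Cohort 1.

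Section 3.1.6 (Stopping Rules) lists the same two sICH triggers (2 per dose level, and "4 cases of sICH in active-treated subjects cumulatively across dose levels"), together with non-ICH major bleeding and discretionary halts. If any listed criterion is met, with sICH across dose groups expressly included, "escalation to a higher dose level will not proceed". After review, one of three recommendations follows: terminate, continue at a modified dose, or "Continue with the study but expand either the current or next cohort by an appropriate number (8 to 16) of subjects". The third carries no condition on dose.

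Section 11.10 explains the rule by reference to small dose-cohort studies of tissue plasminogen activator: "The incidence of sICH observed is about 16% per dose level in these studies". The aim is to avoid a higher incidence than that.

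**The concern.** When a per-dose criterion has been met, the current cohort is the dose at which it was met. Expanding it gives that dose to more subjects, an outcome that Section 3.1.2 does not name. A safety review working from Section 3.1.2 would choose between stopping and going down. A review working from Section 3.1.6 could also stay where it is.

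The primary objective is safety, and these rules govern the three highest doses: 2.4, 4.8 and 9.6 mg. In Cohorts 1 and 2, same-dose expansion comes after one case, before the limit is met. In Cohorts 3 to 5 the cohort already has its 12 active subjects, so expansion would take place after the limit is met, and no new per-dose limit is given. The term *next cohort* is also awkward, because the next planned cohort after Cohort 3 or 4 is at a higher dose, which the same section bars.

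**Working it through.** The plan has no figure of its own to reproduce here. The check is a comparison of texts, followed by an illustration.

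**Options named after an sICH criterion is met in Cohorts 3 to 5**

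| | Section 3.1.2 | Section 3.1.6 |
|---|---|---|
| Higher dose | barred | barred |
| Terminate | named for 2 of 12; not mentioned for 4 cumulative | named |
| Lower dose | named for both triggers | named, as a modified dose (the example given is a lower one) |
| Expand at the same dose | not named | permitted (current cohort) |
| Expand the next cohort | not named | permitted, dose not stated |

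**Where no mismatch arises.** For Cohorts 1 and 2, Section 3.1.2 defers to Section 3.1.6. Non-ICH major bleeding and discretionary halts appear only in Section 3.1.6.

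**Size of an expansion.** The range of 8 to 16 subjects is from Section 3.1.6 and the 3:1 allocation from Section 3.1.2; I assume the ratio is kept. Active subjects added: 8 × 3/4 = 6, up to 16 × 3/4 = 12. Total active at that dose: 12 + 6 = 18, up to 12 + 12 = 24.

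**Limits still in force.** The per-dose limit of 2 has been reached. With 2 cases at the current dose and none earlier, the cumulative rule needs 4 − 2 = 2 more. If the cumulative rule was itself the trigger, it sets no further limit.

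**Illustration.** Take sICH as independent between subjects with true rate p among n further active subjects. The documents give no sICH rate for DS-1040b. I therefore show 5% and 10% (both assumed) and the 16% reference from Section 11.10.

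- Chance of at least one further case: 1 − (1 − p)^n
- Chance of at least two: 1 − (1 − p)^n − np(1 − p)^(n−1)
- Expected further cases: np

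| p | At least 1, n = 6 / 12 | At least 2, n = 6 / 12 | Expected, n = 6 / 12 |
|---|---|---|---|
| 5% | 26% / 46% | 3% / 12% | 0.3 / 0.6 |
| 10% | 47% / 72% | 11% / 34% | 0.6 / 1.2 |
| 16% | 65% / 88% | 25% / 59% | 0.96 / 1.92 |

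For example, at p = 16% and n = 6: 1 − 0.84^6 = 0.649.

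The n = 12 values in the at-least-2 column are also the chance that a cohort of 12 active subjects meets the per-dose rule in the first place: 12%, 34% and 59%. The trigger itself is 2/12 = 16.7%, about the reference incidence.

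**The case against.** The best defence is that this is an incomplete list and not a contradiction. Section 3.1.2 says what the study *may* do; it never says *only* and does not forbid expansion. Section 3.1.6 is the dedicated stopping section and is worded as a directive, so Section 3.1.2 could be read as its summary. This stands in part. But the only continuation that Section 3.1.2 names is at a lower dose, and for Cohorts 3 to 5 it does not point to Section 3.1.6 or say which section prevails.

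It can also be argued that expansion was meant for the non-bleeding or non-ICH triggers, or that staying at the dose is reasonable when 2 of 12 lies close to the 16% reference. The first is not what the text says, since the list follows any criterion and sICH is named. The second is a fair clinical position. If the sponsor holds it, both sections should say so, with a limit attached. The routine between-cohort review in Section 3.1.2 does allow a dose to be repeated, but that sentence concerns ordinary escalation decisions and not a criterion that has been met.

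Three stronger readings are tempting and not supported:

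- A reader might infer that *next cohort* opens a route to a higher dose. Section 3.1.6 rules that out in the sentence introducing the list.
- A reader might infer that sICH cases in an expansion still under way escape the cumulative rule, because Section 3.1.2 speaks of cases where "4 or more cases of sICH in the active-treated subjects are observed across all completed cohorts". That sentence also applies the rule at any time during the study, and Sections 3.1.6 and 11.10 state it with no condition on completion.
- A reader might take the percentages above as the harm caused by the mismatch. They describe any 6 to 12 active subjects at the stated rates. Section 3.1.2 itself allows further subjects to be treated at a lower dose, and the documents give no dose-specific rates from which to calculate a difference.

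**Conclusion.** The mismatch is in the current text and should be corrected. It is confined to Cohorts 3 to 5 and to the two sICH triggers. It comes down to one question: may more subjects receive the dose that met the criterion? Section 3.1.2 points to no, Section 3.1.6 permits it, and no per-dose sICH limit is defined for the 18 to 24 active subjects who would then have been treated at that dose.

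Expansion is not automatic. It would follow an in-depth safety review, and a discretionary halt remains available. The illustrative chance of at least one further sICH, 26% to 46% at 5% and 65% to 88% at 16%, depends on an assumed rate or on one borrowed from tissue plasminogen activator, on independence between subjects, and on the review choosing to expand. It shows that further cases would be quite possible; it does not measure excess risk over a lower dose. The conclusion rests on the wording and does not depend on these figures.

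**What to change.** Use one list of permitted actions in both sections, and add to Section 3.1.2 a reference to Section 3.1.6 for Cohorts 3 to 5.

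In Section 3.1.6, state that:

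- after an sICH criterion is met in Cohorts 3 to 5, any continued or expanded cohort is at a dose below the current dose level; for the cumulative trigger, below the dose being given when the fourth case occurs;
- *next cohort*, after any stop, is never at a higher dose.

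Keep same-dose expansion for non-ICH major bleeding and discretionary halts. Leave Cohorts 1 and 2 as they are.

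If the sponsor wishes to keep same-dose expansion after an sICH stop, say so in both sections and set an explicit further sICH limit for the expanded group.

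The cost is wording in two sections, with no new data or procedures. The real loss is the option to gather more same-dose data after an sICH stop or, under the alternative, a tighter condition on using it.

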3.2. Selection of Doses

3.2.1. Experimental Treatments

This study will enroll subjects into cohorts as outlined in Section 3.1.2.

In this study, a range of single, IV doses will be evaluated during the dose escalation. The starting dose of 0.6 mg (loading dose of 0.15 mg as 0.5-hour IV infusion, followed by a maintenance dose of 0.45 mg as 5.5-hour IV infusion), was selected based on safety, PK, and PD data from a healthy volunteer (including elderly subjects) study (DS1040-A-U101).

Based on human PK data, the projected maximum (peak) observed concentration in circulating blood (C_{max}) and area under the plasma concentration-time curve (AUC) of the 0.6 mg starting dose in a typical subject with a body weight of 75 kg and a creatinine clearance of 90 mL/min are: 13.2 ng/mL and 118 ng·h/mL, respectively, which are 1.2% and 1.5% of the highest exposure achieved in healthy young subjects (mean C_{max} = 1102 ng/mL in the 12 mg 0.5-hour IV infusion dose level and mean area under the concentration-versus-time curve from time 0 extrapolated to infinity [AUC_{inf}] = 8116 ng·h/mL in the 40 mg 24-hour IV infusion dose level), and 2.6% and 10.4% of the highest exposure achieved in elderly subjects (mean C_{max} = 505 ng/mL and mean AUC_{inf} = 1135 ng·h/mL in the 6 mg 0.5-hour IV infusion dose level). Projected plasma exposure levels for planned doses are summarized in Table 3.2. Based on human biomarker data, the projected PK exposure at the starting dose of 0.6 mg will likely result in an approximately 15% reduction in clot lysis time.

The maximum dose of 9.6 mg (loading dose of 2.4 mg as 0.5-hour IV infusion, followed by maintenance dose of 7.2 mg as 5.5-hour IV infusion) was selected to achieve full effect on clot lysis time reduction. Projected C_{max} and AUC_{inf} are 212 ng/mL and 1889 ng·h/mL, respectively, which are 19% and 23% of the highest exposure achieved in healthy, young subjects, and 42% and 166% of the highest exposure achieved in elderly subjects.

Table 3.2: Projected Plasma Pharmacokinetic Parameters

Cohort	Total Dose (mg)	Loading Dose (mg) over 0.5 hours	Maintenance Dose (mg) over 5.5 hours	Simulated Plasma PK Parameters			
				C _{0.5h} (ng/mL)	C _{6h} (C _{max}) (ng/mL)	t _{max} (h)	AUC (ng·h/mL)
1	0.6	0.15	0.45	11.9	13.2	6	118
2	1.2	0.3	0.9	23.8	26.5	6	236
3	2.4	0.6	1.8	47.7	52.9	6	472
4	4.8	1.2	3.6	95.3	106	6	944
5	9.6	2.4	7.2	191	212	6	1889

AUC = area under the plasma concentration-time curve C_{0.5h} = maximum plasma concentration at 0.5 hours; C_{6h} = maximum plasma concentration at 6 hours; PK = pharmacokinetic; t_{max} = time of maximum observed concentration.

Simulation assumptions: body weight = 75 kg, CL_{cr} = 90 mL/min

3.2.2. Control Treatments

The placebo for DS-1040b will be 0.9% Sodium Chloride Injection, USP and will be provided by the site. In order to maintain the blind, placebo (0.9% Sodium Chloride Injection, USP) will be administered in the same manner as DS-1040b in the respective cohorts. The detailed procedures for drug preparation will be provided separately in the pharmacy manual.

4. STUDY POPULATION

The study population will comprise male and female subjects 18 to 80 years of age, inclusive, with a clinical diagnosis of ischemic stroke with middle cerebral artery (MCA) occlusion (M1 or M2), as demonstrated by computed tomography (CT) or magnetic resonance (MR) angiography, who experienced stroke symptom onset within 3 to 8 hours prior to the initiation of study drug administration (for wake-up strokes, symptom onset time refers to last time the subject was known to be well).

4.1. Enrollment

Investigators will maintain a confidential screening log of all potential study candidates that includes limited information of the subjects (initials, age, sex) and the date and outcome of the screening process (eg, enroll in the study, reason for ineligibility, refused to participate).

Investigators will be expected to maintain an Enrollment Log of all subjects enrolled in the study, indicating their assigned randomization number.

Investigators will maintain a confidential subject identification code list. This confidential list of names of all subjects allocated to randomization numbers on enrolling in the study, allows the Investigator to reveal the identity of any subject when necessary.

Each subject or legally acceptable representative will be provided with information about the study, will have all questions answered to their satisfaction, and will sign and date an ICF. This will be completed before any study-specific procedures are performed. Additional information about informed consent procedures is provided in Section 1.5.2.

4.1.1. Inclusion Criteria

Subjects must satisfy all of the following criteria to be included in the study:

1. Subjects have a clinical diagnosis of ischemic stroke MCA occlusion (M1 or M2), as demonstrated by CT or MR angiography.
2. Men and women 18 to 80 years of age, inclusive.
3. Subjects have stroke symptom onset within 3 to 8 hours before initiation of study drug administration. For subjects with a wake-up stroke, symptom onset time refers to the last time the subject was known to be well.
4. Subjects have a NIHSS score > 4 and < 22 .
5. Subjects have a body weight of 50 kg to 120 kg, inclusive.
6. Subjects, or their legally authorized representative, must give written informed consent to participate in the study prior to participating in any study-related procedures. A separate written informed consent is required for collecting a blood sample for genotyping.

4.1.2. Exclusion Criteria

Subjects who meet any of the following criteria will be disqualified from entering the study:

1. Subjects have evidence of intracranial hemorrhage on noncontrast CT (or MR).
2. Subjects have symptoms of subarachnoid hemorrhage, even with normal CT.
3. Subjects have evidence of large MCA territory infarction (sulcal effacement or blurring of gray-white junction in greater than 1/3 of MCA territory).
4. Subjects have prior non-traumatic intracranial hemorrhage.
5. Subjects have known arteriovenous malformation or aneurysm.
6. Subjects have evidence of active bleeding.
7. Subjects have platelet count < 100,000.
8. Subjects have INR > 1.7.
9. Subjects have used heparin within 48 hours or have an elevated partial thromboplastin time.
10. Subjects have used a nonvitamin K antagonist oral anticoagulant such as dabigatran, rivaroxaban, apixaban, or other factor Xa inhibitors within 48 hours.
11. Subjects have used fondaparinux or low molecular weight heparin at an anticoagulation dose within 48 hours.
12. Subjects with anticipated use of heparin, or fondaparinux or low molecular weight heparin, or nonvitamin K antagonist oral anticoagulant such as dabigatran, rivaroxaban, apixaban, or other factor Xa inhibitors within 48 hours of randomization.
13. Subjects have blood pressure > 185/110 mmHg, or require aggressive medication to maintain blood pressure below this limit (routine medical treatment is allowed to lower the blood pressure below this limit).
14. Subjects have had intracranial surgery, clinically significant head trauma (in the opinion of Principal Investigator), Alteplase treatment, or a previous stroke within 3 months.
15. Subjects have had major surgery within 14 days.
16. Subjects have had gastrointestinal or genitourinary bleeding in the last 21 days.
17. Subjects have had a lumbar puncture (or epidural steroid injection) within 14 days.
18. Subjects have a preexisting disability classified by mRS > 1.
19. Subjects have an estimated glomerular filtration rate (using Modification of Diet in Renal Disease [MDRD] equation) < 60 mL/min/1.73 m².
20. Subjects have baseline hemoglobin < 10.5 g/dL.

21. Subjects have a positive pregnancy test. Serum pregnancy tests will be performed in women of childbearing potential (childbearing potential is assumed in women up to 55 years of age).
22. Subject is currently participating in another investigational study or has participated in an investigational drug study within 30 days or 5 half-lives of that investigational drug prior to administration of the study drug.
23. Any other reason, in the opinion of the Investigator, which precludes subject participation in the study.

